## 12.1.2 Hypotheses and Statistical Methods for Secondary Objectives

### 12.1.2.1 Immunogenicity

#### 12.1.2.1.1 Hypotheses

##### *Superiority of QIV-HD to TIV-HD1 or TIV-HD2*

The superiority analyses will be demonstrated in all subjects. For each B strain, the immunogenicity of QIV-HD will be compared to that of TIV-HD group which does not contain the corresponding B strain.

A superiority approach will be used to compare post-vaccination GMTs and seroconversion rates between groups using a 1-sided test with Type I error rate of 0.025 following the individual hypotheses:

$$H_0^s : \frac{GMT_{QIV-HD}^s}{GMT_{TIV-HD}^s} \leq 1.5$$

$$\Leftrightarrow \log_{10}(GMT_{QIV-HD}^s) - \log_{10}(GMT_{TIV-HD}^s) \leq \log_{10}(1.5)$$

$$H_A^s : \frac{GMT_{QIV-HD}^s}{GMT_{TIV-HD}^s} > 1.5$$

$$\Leftrightarrow \log_{10}(GMT_{QIV-HD}^s) - \log_{10}(GMT_{TIV-HD}^s) > \log_{10}(1.5)$$

$$H_0^s : \pi_{QIV-HD}^s - \pi_{TIV-HD}^s \leq 0.1$$

$$H_A^s : \pi_{QIV-HD}^s - \pi_{TIV-HD}^s > 0.1$$

with:

- s: strain in {B1 and B2}
- If s = B1, TIV-HD represents the TIV-HD2 group
- If s = B2, TIV-HD represents the TIV-HD1 group
- $\pi$ : The seroconversion rate

##### *Immunogenicity by HAI Method*

No hypotheses will be tested.

##### *Immunogenicity by SN Method*

No hypotheses will be tested.

### 12.1.2.1.2 Statistical Methods

Assuming that  $\log_{10}$  transformation of the data follows a normal distribution, the  $\log_{10}(\text{data})$  will be used for the statistical analysis, then antilog transformations will be applied to the results of calculations, in order to provide the results in terms of GMs.

#### *Superiority of QIV-HD to TIV-HD1 or TIV-HD2*

The statistical methodology will be based on the use of the 2-sided 95% CI of the ratio of post-vaccination GMTs and difference in seroconversion rates between the QIV-HD group and TIV-HD group. The 95% CIs will be calculated using normal approximation of log-transformed titers for GMTs and using the Newcombe-Wilson score method without continuity correction for seroconversion rates. For each strain, the 2-sided 95% CI should lie above 1.5 for GMTs and above 10% for seroconversion rates.

The superiority objective will be achieved if the superiority is demonstrated for both B strains and for both GMTs and seroconversion rates. Analyses will be performed for both FAS and PPAS but the conclusion will be made from FAS results.

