## 2.2 Secondary Objectives

### *Immunogenicity*

- 1) To demonstrate that each B strain in QIV-HD induces an immune response (as assessed by HAI GMTs and seroconversion rates) that is superior to the response induced by the TIV-HD that does not contain the corresponding B strain in all subjects.
- 2) To describe the immune response induced by QIV-HD, TIV-HD1, and TIV-HD2 by HAI measurement method in all subjects.
- 3) To describe the immune response 28 days after vaccination by virus SN measurement method in a randomized subset of subjects from each study group.

The endpoints for the secondary immunogenicity objectives are presented in [Section 9.2.1.1.1](#) for the HAI method and in [Section 9.2.1.1.2](#) for the SN method.

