## 12.5 Determination of Sample Size and Power Calculation

A total of 2616 adults aged 65 years and older will be enrolled. A sample size of 2616 is determined based on an overall power of 90% for demonstrating non-inferiority for both the HAI GMTs and seroconversion rates comparing QIV-HD vs TIV-HD1 and / or TIV-HD2 for all 4

virus strains. The non-inferiority margins are defined as 1.5 for GMTs and 10% for seroconversion rates.

Assumptions for the above calculations are:

- The expected seroconversion rates for the 4 strains: 45% for A1 strain, 70% for A2 strain, and 40% for both B strains.
- Assumed standard deviations for HAI GMTs are 0.63 for both A strains and 0.55 for both B strains.
- An 8% attrition rate which provides approximately 2407 evaluable adults for immunogenicity analysis.

Based on current sample size, there is 55.4% power to detect the superiority of each B strain comparing QIV-HD groups versus either the TIV-HD1 or TIV-HD2 group in the secondary objective. It is based on an assumption of expected GMT ratio of 1.8 with a standard deviation of 0.55, seroconversion rate of 8% in the group without the B strain and 22% increase in the group with the B strain, and a 5% attrition rate in FAS.

A subset of 300 subjects with 100 subjects from each group will be randomly selected for SN testing.

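### Superiority on the B strains is all-or-nothing; a Hochberg second step would add a controlled single-strain conclusion and leave the both-strain conclusion untouched

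*Protocol*

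**What the plan says.** Protocol 2.2 words the objective per strain: "To demonstrate that each B strain in QIV-HD induces an immune response" that is superior to that of the TIV-HD lacking the strain. Section 12.1.2.1.1 then states hypotheses for B1 (against TIV-HD2) and B2 (against TIV-HD1), "using a 1-sided test with Type I error rate of 0.025 following the individual hypotheses".

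Section 12.1.2.1.2 sets the criterion: "For each strain, the 2-sided 95% CI should lie above 1.5 for GMTs and above 10% for seroconversion rates". It gives one decision rule, repeated in the Synopsis: "The superiority objective will be achieved if the superiority is demonstrated for both B strains and for both GMTs and seroconversion rates". The conclusion is drawn from the FAS.

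Section 12.5 states that "there is 55.4% power to detect the superiority of each B strain".

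The protocol gives no testing order and no fallback, and does not say what status one strain has if only the other fails. The supplied SAP is confined to the additional ELLA assay and refers to a SAP core body that is not among the documents.

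**The concern.** Each superiority comparison asks whether the added B strain produces a response that the trivalent vaccine without it does not. The primary non-inferiority tests do not answer this, because for each B strain they use the TIV-HD group that contains the strain.

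Under the joint rule, a strain that clears both margins gets no formal conclusion if the other strain falls short on GMT. With power only a little above one half, that is a likely outcome. The evidence for the passing strain may be sound, but the protocol provides no error-controlled way to state it.

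**Working it through.** **Inputs.** Group sizes are 1744 and 436 (protocol 5.1.1 and Table 6.1). Section 12.5 gives the rest:
- "It is based on an assumption of expected GMT ratio of 1.8 with a standard deviation of 0.55", taken as the log10 scale;
- "seroconversion rate of 8% in the group without the B strain and 22% increase in the group with the B strain", read as 8% versus 30%;
- "a 5% attrition rate in FAS".

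The FAS is then 1744 × 0.95 ≈ 1657 against 436 × 0.95 ≈ 414. One-sided alpha is 0.025, and the margins are 1.5 and 10 percentage points.

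**GMT, one strain.**
- SE = 0.55 × √(1/1657 + 1/414) = 0.0302.
- Distance from the margin = log10(1.8/1.5) = 0.0792, or 2.62 SE.
- Power at 0.025 = Φ(2.62 − 1.96) = 74.5%.
- Power at 0.0125 = Φ(2.62 − 2.241) = 64.8%.

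**Seroconversion, one strain.** SE = √(0.30 × 0.70/1657 + 0.08 × 0.92/414) = 0.0175. Power = Φ(0.12/0.0175 − 1.96), above 99.99%. GMT therefore decides the outcome.

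**The plan's own figure.** Both strains, treated as independent: 0.7454² = 55.6%, against 55.4% stated. The stated figure is thus the joint power for both strains; it does not reproduce as power for one strain (74.5%).

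**How the present rule fails.**
- At least one strain misses: 1 − 0.556 = 44.4%.
- Exactly one misses: 2 × 0.7454 × 0.2546 = 38.0%.
- Both miss: 0.2546² = 6.5%.

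**Adding a Hochberg second step.** Step 1 is the present rule. In step 2, reached only if step 1 fails, a single strain is concluded superior if it passes both endpoints at one-sided 0.0125. Requiring both endpoints gives each strain one valid test, its weaker result.
- Both strains: 55.6%, unchanged.
- At least one strain: 0.556 + 2 × 0.648 × 0.2546 = 88.5%, a gain of 33 points.

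**Dependence.** The two contrasts use different TIV-HD groups and share only the QIV-HD arm. At 4:1, their correlation is ρ × (1/4)/(1/4 + 1) = 0.2ρ, where ρ is the within-subject correlation of the two B-strain titers. The documents give no ρ, so the range 0 to 1 is assumed:

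| Correlation of the strain statistics | Both strains | At least one, present rule | At least one, with step 2 | One-sided familywise error, both nulls true |
|---|---|---|---|---|
| 0 | 55.6% | 55.6% | 88.5% | 2.50% |
| 0.12 | 56.8% | 56.8% | 86.9% | 2.49% |
| 0.2 | 57.7% | 57.7% | 85.8% | 2.48% |

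Error is calculated for the GMT tests; also requiring seroconversion cannot raise it. With one true null and the other strain certain to pass, it is 2.50%. At a correlation of −0.2 it is 2.502%, so the procedure's condition of non-negative dependence is not a practical difficulty.

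**Illustration with an assumed weaker strain.** If one strain's true ratio were 1.6 (not a figure in the documents) and the other's 1.8, the chance of any formal conclusion would be about 11% under the present rule and 69% with step 2.

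**The case against.** The strongest defence is that nothing here is wrong. Requiring both strains and both endpoints is an intersection-union test that holds the error at one-sided 0.025. The primary objective is built the same way, and the product is meant to cover both B lineages. Wording the objective for each strain can mean every strain, so it does not contradict the joint rule. The stated 55.4% reproduces as joint power, so the failure risk was in effect disclosed and accepted for a secondary objective. All of this stands: the point concerns efficiency and clarity.

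A reader might also infer more than the documents support:
- **That 44% is the chance of one narrow miss.** It is the chance of at least one miss of any size and includes the 6.5% where both strains miss.
- **That no B-strain conclusion survives.** Only the formal superiority conclusion is withheld. Per-strain intervals are produced in the FAS and PPAS, and each B strain has its own non-inferiority tests.
- **That the plan carries a 4.9% familywise error.** That figure (1 − 0.975²) belongs to claiming either strain separately at 0.025. The protocol authorises no such claim.
- **That the full analysis plan has no fallback.** The SAP core body was not supplied, so this cannot be said.

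The defence does not show any cost to adding step 2. Because step 1 is the present rule, the both-strain conclusion loses nothing.

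**Conclusion.** The point holds as a free improvement. The present rule is valid, but on the planning assumptions it gives a formal superiority conclusion in only about 56% of trials. In a further 38% exactly one strain passes, and the protocol gives that strain no formal status. A Hochberg second step raises the chance of at least one formal strain-level conclusion to about 86–89% (correlation 0.2 to 0), keeps the both-strain chance as it is, and holds one-sided familywise error at about 2.5%.

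This rests on the values in protocol 12.5, a normal approximation for log10 titers, and an assumed range for the correlation between strains. It is limited to the protocol text; the SAP core body could already contain a fallback.

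**What to change.** Amend protocol 12.1.2.1.2 and the matching Synopsis text before unblinding, and align the SAP core body if it does not already provide for this:

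1. If the 2-sided 95% CIs clear 1.5 for the GMT ratio and 10% for the seroconversion difference for both B strains, conclude superiority for both, as now.
2. Otherwise, conclude superiority for a single B strain if its 2-sided 97.5% CIs clear both 1.5 and 10%.

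Do not attach a further claim that intervals above 1 and above 0 show superiority without the margin. The two steps do not cover it: with true ratios of 1.5 and 1.0, adding such a claim gave a familywise one-sided error of about 3.7% in a GMT-only simulation, even with Hochberg reapplied at a ratio of 1.

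The cost is a few lines of wording and one extra set of 97.5% intervals, with no added subjects, no additional alpha and no loss of power for the both-strain conclusion.

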#### *Immunogenicity by HAI Method*

The percentages of subjects achieving seroprotection and the corresponding 95% CIs (Clopper-Pearson method) (12) will be performed for pre-vaccination (V01) and post-vaccination immunogenicity (V02). The geometric mean titer ratios (GMTRs) will be calculated for post-vaccination immunogenicity (V02) over the baseline immunogenicity (V01) with the corresponding 95% CIs (assuming normal approximation of log-transformed values). Reverse cumulative distribution curves (RCDCs) against each strain will be performed for baseline (V01) and post-vaccination immunogenicity (V02). Additional parameters may be displayed as appropriate.

#### *Immunogenicity by SN Method*

Immunogenicity in terms of GMTs, seroconversion, and percent of subjects with GMTs  $\geq 1/40$  [dil] will be summarized along with their 95% CIs for post-vaccination immunogenicity (V02). The normal approximation of log-transformed titers will be applied to calculate the 95% CIs for GMTs. The 95% CIs will be calculated using Clopper-Pearson method for percentages. The GMTRs will be calculated for post-vaccination immunogenicity (V02) over the baseline immunogenicity (V01) with the corresponding 95% CIs (assuming normal approximation of log-transformed values). RCDCs against each strain will be performed for baseline (V01) and post-vaccination immunogenicity (V02). Additional parameters may be displayed as appropriate.

### 12.1.2.2 Safety

#### 12.1.2.2.1 Hypotheses

No hypotheses will be tested.

#### 12.1.2.2.2 Statistical Methods

Safety results will be analyzed descriptively for subjects in SafAS who received one of the vaccines. Solicited reactions (solicited injection site and systemic reactions), unsolicited AEs, SAEs, and AESIs will be summarized. The main parameters will be described with 95% CIs (Clopper-Pearson method) (12).

- Unsolicited systemic AEs occurring within 30 minutes of injection (immediate unsolicited AEs)
- Solicited injection site reactions (pain, erythema, swelling, induration, and bruising) occurring within 7 days after the day of injection (D0 to D7) according to presence, time to onset, intensity (Grade 1, Grade 2, or Grade 3), number of days of occurrence, action taken, and whether the reaction led to early termination from the trial. When more than 1 intensity level is reported within a time period, the highest intensity will be used
- Solicited systemic reactions (fever, headache, malaise, myalgia, and shivering) occurring within 7 days after the day of injection (D0 to D7) according to presence, time to onset, intensity (Grade 1, Grade 2, or Grade 3), number of days of occurrence, action taken, and whether the reaction led to early termination from the trial. When more than 1 intensity level is reported within a time period, the highest intensity will be used
- Unsolicited AEs occurring within 28 days after injection by system organ class (SOC) and PT, relationship, intensity, time to onset, and duration
- All SAEs that occur throughout the trial by SOC and PT, seriousness criteria, time to onset, outcome, relationship, and whether the SAE led to early termination throughout the trial
- All AESIs reported throughout the trial by SOC and PT and relationship

#### 12.2 Analysis Sets

Four main analysis sets will be used: the PPAS, the FAS, the Expanded Immunogenicity Subset, and the Safety Analysis Set (SafAS).

##### 12.2.1 Full Analysis Sets

The FAS is defined as the subset of randomized subjects who received at least 1 dose of a trial vaccine and had a post-vaccination blood sample HAI result for at least 1 strain. Subjects will be analyzed according to the vaccine group to which they were randomized.

For the assessment of the immune response by virus SN method, the analysis will be performed on the subjects from the FAS randomized into the Expanded Immunogenicity Subset with at least one post-vaccination SN assay result for at least 1 strain.

### 12.2.2 Safety Analysis Set

The SafAS is defined as those subjects who have received study vaccinea. All subjects will have their safety analyzed according to the vaccine they actually received.

Safety data recorded for a vaccine received out of the protocol design will be excluded from the analysis (and listed separately).

### 12.2.3 Per-Protocol Analysis Set

The PPAS is a subset of the FAS. The subjects presenting with at least one of the following relevant protocol deviations will be excluded from the PPAS:

- Subject did not meet all protocol-specified inclusion criteria or met at least one of the protocol-specified exclusion criteria
- Subject did not receive vaccine
- Subject received a vaccine other than the one that he / she was randomized to receive
- Preparation and / or administration of vaccine was not done as per-protocol
- Subject did not provide the post-dose serology sample (V02) in the proper time window (i.e., 28 to 35 days after vaccination) or a post-dose serology sample (V02) was not drawn
- Subject received a protocol-prohibited therapy / medication / vaccine

In addition to the criteria listed above, subjects will also be excluded from the PPAS if their post-vaccination serology sample did not produce a valid HAI test result (i.e., HAI results for all antigens are missing).

The above protocol deviations leading to exclusion from the PPAS may be detailed and completed if necessary in the SAP, following the review of protocol deviations during the study conduct. In any case, the PPAS definition will be finalized before the first database lock.

### 12.2.4 Populations Used in Analyses

All subjects with data in the CRB will be taken into account in the description of the population (e.g., the disposition, the demographic or baseline characteristics).

The safety analyses will be performed on the SafAS.

All immunogenicity analyses from HAI method for primary and secondary objectives will be performed on both FAS and PPAS.

The secondary SN immunogenicity analyses will be performed on the Expanded Immunogenicity Subset.

---

a for which safety data are scheduled to be collected

## 12.3 Handling of Missing Data and Outliers

### 12.3.1 Safety

No replacement will be done. Nevertheless, missing relationship will be considered as related at the time of the statistical analysis. No search for outliers will be performed. In all subject listings, partial and missing data will be clearly indicated as missing.

### 12.3.2 Immunogenicity

In order to appropriately manage replicate values for analysis purposes, the individual GM of all values will be computed for each blood sample after managing extreme values as described. The computed value is then considered the titer for that particular blood sample.

- If a titer is  $< \text{LLOQ}$ , then the computed value,  $\text{LLOQ}/2$ , will be used.
- If a titer is  $\geq \text{LLOQ}$  and  $< \text{ULOQ}$  (or  $\leq \text{ULOQ}$ ), then the titer itself will be used.
- If a titer is  $\geq \text{ULOQ}$  (or  $> \text{ULOQ}$ ), then computed value,  $\text{ULOQ}$ , will be used.

Any other replacement to be applied to specific endpoints will be described in the SAP.

No test or search for outliers will be performed.

No replacement will be done for missing values. Based on the previous TIV-HD and QIV-SD trials in this population, the amount of missing immunogenicity data is expected to be  $\leq 5\%$  in this trial. Usually in vaccine trials, it seems generally reasonable to assume missing immunogenicity data are missing completely at random (MCAR) (13). Indeed, it is highly unexpected that the dropout (or any other reason for missing data) could be linked to the immune response of the subject. Therefore, confirming the results of the PPAS for the primary analysis with the FAS would be satisfactory in terms of sensitivity analysis.

## 12.4 Interim / Preliminary Analysis

The statistical analyses will be performed in 2 steps:

- First step will be the analysis of main HAI immunogenicity and safety results obtained on data collected within approximately 28 days following vaccination (from D0 to Visit 2). The study blind will be broken at that time.
- Second step will be assessing the remaining objectives of the study.

No statistical adjustment for the interim analysis is necessary because there are no repeat analyses of the same hypotheses.

## 12.5 Determination of Sample Size and Power Calculation

A total of 2616 adults aged 65 years and older will be enrolled. A sample size of 2616 is determined based on an overall power of 90% for demonstrating non-inferiority for both the HAI GMTs and seroconversion rates comparing QIV-HD vs TIV-HD1 and / or TIV-HD2 for all 4

virus strains. The non-inferiority margins are defined as 1.5 for GMTs and 10% for seroconversion rates.

Assumptions for the above calculations are:

- The expected seroconversion rates for the 4 strains: 45% for A1 strain, 70% for A2 strain, and 40% for both B strains.
- Assumed standard deviations for HAI GMTs are 0.63 for both A strains and 0.55 for both B strains.
- An 8% attrition rate which provides approximately 2407 evaluable adults for immunogenicity analysis.

Based on current sample size, there is 55.4% power to detect the superiority of each B strain comparing QIV-HD groups versus either the TIV-HD1 or TIV-HD2 group in the secondary objective. It is based on an assumption of expected GMT ratio of 1.8 with a standard deviation of 0.55, seroconversion rate of 8% in the group without the B strain and 22% increase in the group with the B strain, and a 5% attrition rate in FAS.

A subset of 300 subjects with 100 subjects from each group will be randomly selected for SN testing.

## **13 Ethical and Legal Issues and Investigator / Sponsor Responsibilities**

### **13.1 Ethical Conduct of the Trial / Good Clinical Practice**

The conduct of this trial will be consistent with the standards established by the Declaration of Helsinki and compliant with the ICH guidelines for GCP as well as with all local and / or national regulations and directives.

### **13.2 Source Data and Source Documents**

“Source data” are the data contained in source documents. Source documents are original documents or certified copies, and include, but are not limited to, diary cards, medical and hospital records, screening logs, informed consent / assent forms, telephone contact logs, and worksheets. The purpose of trial source documents is to document the existence of subjects and to substantiate the integrity of the trial data collected. Investigators must maintain source documents so that they are accurate, complete, legible, and up to date.

For missing or discrepant data on a diary card, the study coordinator will obtain verbal clarification from the subject, enter the response into the “investigator’s comment” page of the diary card, and transfer the information to the CRB.

The subject pre-screening log should list all individuals contacted by the Investigators to participate in the trial, regardless of the outcome.

The Investigator must printa any electronic records on an ongoing basis, sign and date them immediately after creation, and keep the printouts on file as source documents that can be verified by the Sponsor or an inspector against the electronic records. Any later changes of an electronic record require the record to be re-printed, dated (with an indication of the date of change), and signed. Such records must also be kept together with the original printed copy.

### **13.3 Confidentiality of Data and Access to Subject Records**

Prior to initiation of the trial, the Investigator will sign a fully executed confidentiality agreement with Sanofi Pasteur.

Sanofi Pasteur personnel (or designates), the IECs / IRBs, and regulatory agencies, including the FDA, require direct access to all study records, and will treat these documents in a confidential manner.

In the event a subject's medical records are not at the investigational site, it is the responsibility of the investigator to obtain those records if needed.

